**2 Study Objectives**

The primary outcome measure is time to first relapse defined as recurrence of any signs or symptoms attributable to active vasculitis after a period of complete remission with at least 2 minor or 1 major item on the BVAS score (BVAS $\geq 2$ ). Secondary outcome measures are 1) frequency and severity (as determined by BVAS score) of relapse in each group; 2) time to positive ANCA; 3) frequency and severity of infections; 4) time to IL-10 secreting B regulatory cells  $> 45\%$  or CD5+ B cells  $> 43\%$  of total B cells.

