B cell subsets will be measured in the UNC Hospitals clinical lab as per our standard of care after treatment with rituximab. We will measure % of CD19+ by flow cytometry. A sample will be obtained for research analysis with each clinical sample to determine the %CD19+CD5+ B cells. For study inclusion, we will require a minimum threshold of 50 CD5+CD19+ **total detectable** events to assess this percentage. In the WATCH group, the first sample will be obtained at the time of enrollment, 6, and 12 weeks later and then at every visit subsequently until CD19+ B cell are  $\geq 1\%$ . In the maintenance therapy group, B cell subsets will be measured at the time of enrollment, and prior to each Rituximab infusion until Month 24. For subjects on maintenance therapy with azathioprine or mycophenolate mofetil, B-cell subsets will be measured at enrollment, week 22, week 46, week 70 and week 94.. Detailed B cell phenotyping and measure of IL-10 production will be performed at the same time as CD5+ analysis.

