### **3.3 Secondary Study Endpoints**

Secondary outcome measures are 1) frequency and severity (as determined by BVAS score) of relapse in each group; 2) time to positive ANCA; 3) frequency and severity of infections; 4) time to relapse after IL-10 producing B cells  $> 45\%$  of total B cells, compared to when CD5+ B cells are  $> 43\%$  of total B cells.

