### 7.1 Sample Size Determination

Based on our ANCA cohort registry, we estimate being able to enroll 40 eligible patients over a period of 24 months. Based on our previous studies, we estimate that ~31 patients (78%) will recover  $\geq 43\%$  CD5+ B cells after induction therapy and will be randomized to maintenance vs NO maintenance immunosuppressive therapy arm. We anticipate 9 patients (22%) will fall in the “low” CD5+ B cell category and will receive maintenance therapy with rituximab, azathioprine or mycophenolate mofetil.

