### 7.2 Statistical Methods

As a proof-of-concept trial, no statistical comparisons will be done, but summary statistics and graphical displays of the data will be observed for patterns and also used to calculate sample size estimates needed for statistical comparisons in a larger trial. Summary statistical estimates of population parameters will be tabulated along with corresponding confidence intervals (CIs).

For the descriptions of each analytic Aim below groups, will be defined as follows:

Cohort 1: Subjects in remission with CD19+CD5+  $\geq 43\%$

- A) To discontinue maintenance immunosuppression (NO-Maintenance Therapy Group)
- B) To continue on maintenance immunosuppression (Maintenance Therapy Group)

Cohort 2: Subjects in remission with CD19+CD5+  $< 43\%$

- B) To continue on maintenance immunosuppression (Maintenance Therapy Group)

Aim 1. Characterize and compare A and B in terms of the outcome variables, based on data from Cohort 1.

Aim 2. Characterize and compare A and B in terms of the outcome variables, based on Cohorts 1 and 2 combined.

Aim 3. Characterize and compare Cohort 1(B) and Cohort 2(B).

Aim 4. Characterize and compare Cohort 1(A) and Cohort 2(B).

Aim 5. Obtain point- and interval-estimates needed to plan a future confirmatory randomized clinical trial.

Time to first relapse – we will summarize the time (months) to relapse and plot Kaplan-Meier curves for time to FIRST relapse by each regimen and cohort, and calculate median time to relapse and a 24-month relapse-free survival rate for each group. We will calculate a univariate hazard ratio with 95% confidence interval using Cox regression models. No statistical analyses for comparisons will be done, but trends and relapse estimates by regimen and by cohort will be used for formulating a larger study. We are most interested in time to first relapse as that denotes a clinical end point for the study since it will require reinitiating induction therapy rather than maintenance or “no maintenance”. However, we will continue to collect data on subjects with relapses for their full follow-up time to have some information on how these subjects respond to treatment and/or if they relapse again after being in this study.

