Time to first positive ANCA test (among those negative at randomization) – The percent who develop a positive ANCA test, and timing to a positive ANCA test will be summarized, with plots of time to this event using Kaplan-Meier curves generated. No statistical analyses for comparisons will be done, but trends and estimates by regimen and by cohort will be used to inform a larger study.

Frequency (number) and severity (by BVAS) of relapse – Among those who relapse, we will evaluate which organs are impacted by disease relapse (using BVAS subsections) and the severity of the relapse

(summarized by the BVAS score). This will be done by regimen and by cohort. Zero in any organ sub-section shows no disease activity in that organ. The total score range for a BVAS is 0 to 64. No statistical analyses are planned, but this will provide information for potential patterns of relapse in specific organs as well as information on the severity of relapses by group.

Occurrence of any infection – all infections will be counted and described by regimen and by cohort.

Frequency/severity/etiology of infections – recurrent infections, severity of infections, with those requiring hospitalization and/or intravenous antibiotics deemed as serious—with etiology of each infection listed. Etiologies will be listed as reported and may include a combination of location (urinary tract, upper respiratory, lung) and type of pathogen (bacterial, viral, fungal or parasitic). All infection metrics (recurrent, severity and type) be described and tallied within each regimen and cohort, but no statistical comparisons will be done. This information is necessary to understand the expected infectious adverse events that can be expected in a larger study.

Frequency and severity of any adverse advent (AEs and SAEs) – These will be catalogued as above for infections – including type of event, relation to therapy/discontinuation of therapy, and outcome of adverse event.

Time to B-cell normalization (that is, % IL-10 Secreting > 45% or % CD5+ B Cells Response > 43%) – the number who normalize will be evaluated; time to normalization will be observed in Kaplan-Meier plots by each regimen and cohort, but no statistical tests will be done to compare groups. These measures will guide the optimal times for follow-up and monitoring in a larger study.

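### Time to B-cell normalisation uses the criterion that selects Cohort 1, so its CD5+ or composite curves are uninformative in both randomised arms, and secondary endpoint 4 is defined in two incompatible ways

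*Combined protocol and SAP*

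**What the plan says.** **Event and display.** Section 7.2 counts a patient as normalised when IL-10-secreting B cells exceed 45% or CD5+ B cells exceed 43%. It then states that "time to normalization will be observed in Kaplan-Meier plots by each regimen and cohort", without formal tests, and that the results are to guide follow-up and monitoring times in a larger study. No time origin or at-risk set is given. Section 7.3 includes every enrolled subject. By contrast, the ANCA endpoint in Section 7.2 is limited to patients negative at randomisation.

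**Cohorts.** The definition in Section 7.2 opens "Cohort 1: Subjects in remission with CD19+CD5" and sets the threshold at 43% or more. Sections 5.3 and 6 apply the same rule before assignment. Section 3.1 writes the randomisation rule as strictly above 43%.

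**Expected numbers.** Section 7.1 says "we estimate being able to enroll 40 eligible patients over a period of 24 months", then "we estimate that ~31 patients (78%) will recover" at least 43% CD5+ cells, and "We anticipate 9 patients (22%) will fall in the" low category.

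**Endpoint 4.** Section 2 lists "time to IL-10 secreting B regulatory cells" above 45%, or CD5+ cells above 43%. Section 3.3 lists "time to relapse after IL-10 producing B cells" exceed 45%, compared with when CD5+ cells exceed 43%. The Study Summary names two secondary outcomes, and neither is this one.

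**WATCH sampling.** Section 3.1 takes samples at enrolment and 6 and 12 weeks later, "then at every visit subsequently until CD19+ B cell are" at or above 1%.

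**The concern.** A time-to-event curve needs patients who are event-free at its origin. Here one sufficient limb of the event is, apart from the inequality sign, the criterion that puts a patient into the randomised cohort. For this outcome, Aim 1 (the two regimens within Cohort 1) would compare two curves that have both already fallen. Aims 3 and 4 would contrast cohorts that differ at time zero by construction. Aim 2 would mix time-zero events with genuine later ones in the maintenance curve. The plan intends to use these displays to set monitoring times for the next trial.

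The two versions of endpoint 4 are different variables. One ends at a laboratory threshold. The other starts from a threshold and ends at relapse. A reader cannot tell which will be reported, and the second has no planned analysis.

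**Working it through.** **1. Reproduce the plan's split (Section 7.1).**
- Cohort 1: 40 × 0.78 = 31.2, about 31; 31/40 = 77.5%.
- Cohort 2: 40 × 0.22 = 8.8, about 9; 9/40 = 22.5%.

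The plan's figures of 31 and 9 reproduce.

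**2. Kaplan-Meier value just after time zero.** Take randomisation (assignment for Cohort 2) as origin and the composite or CD5+ event. With d₀ events at time zero among n₀ patients, S(0+) = 1 − d₀/n₀.

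| Group | n₀ | d₀ | S(0+) |
|---|---|---|---|
| Cohort 1, all | 31 | 31 | 1 − 31/31 = 0 |
| Either randomised arm | 15 or 16 | 15 or 16 | 0 |
| All patients | 40 | 31 | 1 − 31/40 = 0.225 |
| All maintenance, 15 from Cohort 1 | 15 + 9 = 24 | 15 | 1 − 15/24 = 0.375 |
| All maintenance, 16 from Cohort 1 | 16 + 9 = 25 | 16 | 1 − 16/25 = 0.36 |

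For the composite, the last three rows assume that no Cohort 2 patient enters with IL-10 above 45%. The documents give no figure for this; any such patient lowers the value.

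**3. Sensitivity to the inequality signs.** Entry is at least 43% (Sections 1.4, 5.3, 6 and 7.2), while the event is above 43%. A patient at exactly 43% does not meet the CD5+ limb. If k of 31 are at exactly 43%, and none of those has IL-10 above 45%, S(0+) = k/31: 0.032 for one, 0.065 for two, 0.097 for three. The conclusion does not change.

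**4. What remains after an at-risk restriction.** Limiting CD5+ normalisation to patients not above threshold at randomisation leaves about 40 − 31 = 9, all in Cohort 2 and all on maintenance. Exact 95% intervals for the proportion normalising are wide: 3 of 9 gives 7.5% to 70.1%, and 5 of 9 gives 21.2% to 86.3%.

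**5. Sampling text against the visit table.** CD19+ of at least 1% is already an entry condition (Sections 3.1 and 4.1). Read literally, Section 3.1 therefore gives WATCH samples at enrolment and weeks 6 and 12, and none after that. The WATCH table in Section 6 has no week 6 visit. It draws research blood at weeks 0, 12, 22, 34, 46, 58, 70, 82, 94 and 106, roughly every second visit. The two cannot both be followed.

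**The case against.** **The 'or' may mean two measures, not one composite.** Section 7.2 speaks of measures in the plural, and Section 3.3 sets IL-10 against CD5+. IL-10 above 45% is not an entry criterion anywhere. This stands. A reader might infer that the endpoint carries no information in the randomised cohort, or that only about 9 patients can contribute at all. The documents support that only for the composite or CD5+ event. An IL-10 curve could be informative in all 40.

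**Time zero is inferred.** No origin is stated, and the visit tables have a row for standard-of-care visits until B-cell recovery between enrolment and Visit 1. Counted from enrolment, some times could exceed zero. But Sections 3.1 and 4.1 place enrolment at B-cell recovery, and any such interval would precede assignment and could say nothing about regimen. The missing origin is itself a defect.

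**Sampling.** A reader might infer that Section 3.1 ends WATCH sampling at once. It does not: the samples at weeks 6 and 12 are unconditional, and the stopping clause governs only later visits.

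**Re-normalisation after rituximab in Cohort 1 maintenance patients could be of interest.** It could, but the plan does not define it.

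**Weight.** This is a descriptive secondary display in a trial with no planned testing. That is correct, and it limits the importance of the point.

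**Conclusion.** The point holds for the composite and CD5+ events. With randomisation as origin, about 31 of 40 patients (78% on the plan's own projection) have the event at time zero, except any at exactly 43%. The curves in both randomised arms are then uninformative, and first CD5+ normalisation can be observed only in the roughly 9 Cohort 2 patients. It does not extend to an IL-10-only curve.

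The conflict over endpoint 4 is a direct contradiction between Sections 2 and 7.2 on one side and Section 3.3 on the other. The WATCH sampling text also conflicts with the visit table; taken literally it would end sampling after week 12.

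The conclusion rests on the projected split, on CD5+ being measured before assignment as Sections 5.3 and 6 state, and on randomisation as origin. The primary endpoint is unaffected. The text is wrong as written and should be corrected, because the plan relies on these displays to choose monitoring times later.

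**What to change.** 1. Use one definition of secondary endpoint 4 in Sections 2, 3.3 and 7.2. If time to relapse after threshold is also wanted, list it as a separate endpoint with its own analysis.
2. State randomisation (assignment for Cohort 2) as the time origin.
3. Analyse CD5+ and IL-10 separately, each among patients not above that threshold at randomisation, as the ANCA endpoint already does for its own event. CD5+ normalisation is then in effect a Cohort 2 measure.
4. For Cohort 1, describe CD5+ over time, with time to first evaluable CD5+ below 43% in the WATCH arm. Report the maintenance arm separately: rituximab lyses B cells (Section 1.2), and Section 6.3.2 gives five scheduled draws (weeks 0, 22, 46, 70 and 94) against ten in WATCH. A direct comparison of the arms would be confounded by depletion and by sampling frequency.
5. State when a follow-up sample is evaluable. The 50-event minimum in Section 3.1 is written for inclusion only, so extending it to follow-up needs an explicit decision.
6. Reconcile the above-43% and at-least-43% signs across the cohort rule and the event, and word the loss-of-normalisation event to match.
7. Replace the WATCH sampling sentence in Section 3.1 with a reference to the visit table. Deleting only the stopping clause would leave a draw at every visit, which the table does not schedule.

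The cost is wording in Sections 2, 3.1, 3.3 and 7.2, plus alignment of the threshold sign wherever it appears. No blood draws are needed beyond those already in the visit table.

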### **7.3 Subject Population(s) for Analysis**

**All study subjects enrolled will be included in our analysis.**

## **8 Safety and Adverse Events**

### **8.1 Definitions**

#### **Unanticipated Problems Involving Risk to Subjects or Others**

Any incident, experience, or outcome that meets all of the following criteria:

- Unexpected in nature, severity, or frequency
- Related or possibly related to participation in the research
- Serious (as defined below)

## Adverse Event

An **adverse event** (AE) is any symptom, sign, illness or experience that develops or worsens in severity during the course of the study. Intercurrent illnesses or injuries should be regarded as adverse events. Abnormal results of diagnostic procedures are considered to be adverse events if the abnormality:

- results in study withdrawal
- is associated with a serious adverse event
- is associated with clinical signs or symptoms
- leads to additional treatment or to further diagnostic tests
- is considered by the investigator to be of clinical significance

## Grading the Severity of Adverse Events (Common Terminology Criteria for Adverse Events v.4.0[CTCAE])

### Grades

Grade refers to the severity of the AE. The CTCAE displays Grades 1 through 5 with unique clinical descriptions of severity for each AE based on this general guideline:

- **Grade 1:** Mild; asymptomatic or mild symptoms; clinical or diagnostic observations only; intervention not indicated.
- **Grade 2:** Moderate; minimal, local or noninvasive intervention indicated; limiting age-appropriate instrumental activities of daily living\*. An infection requiring oral antibiotics and resulting in interruption of school or work ≤1 day, is considered a Grade 2 infection.
- **Grade 3:** Severe or medically significant but not immediately life-threatening; hospitalization or prolongation of hospitalization indicated; disabling; limiting self-care activities of daily living\*\*. An infection requiring hospitalization or IV antibiotics or resulting in interruption of school or work > 1 day will be considered a Grade 3 infection
- **Grade 4:** Life-threatening consequences; urgent intervention indicated.
- **Grade 5:** Death related to AE.

\*Instrumental activities of daily living refer to preparing meals, shopping for groceries or clothes, using the telephone, managing money, etc.

\*\*Self-care activities of daily living refer to bathing, dressing and undressing, feeding self, using the toilet, taking medications, and not bedridden.

## Serious Adverse Event

Adverse events are classified as serious or non-serious. A **serious adverse event** is any AE that is:

- fatal
- life-threatening
- requires or prolongs hospital stay
- results in persistent or significant disability or incapacity
- a congenital anomaly or birth defect
- an important medical event

Important medical events are those that may not be immediately life threatening but are clearly of major clinical significance. They may jeopardize the subject and may require intervention to prevent one of the other serious outcomes noted above. For example, drug overdose or abuse, a seizure that did not result in in-patient hospitalization, or intensive treatment of bronchospasm in an emergency department would typically be considered serious.

All adverse events that do not meet any of the criteria for serious should be regarded as ***non-serious adverse events***.

**For the purpose of this trial, any of the signs, symptoms, or conditions listed under warnings and adverse reactions for rituximab, azathioprine and mycophenolate mofetil under section 1.2 will be considered expected adverse events:**

### **Adverse Event Reporting Period**

The study period during which adverse events will be reported will be defined as the period from the initiation of any study procedures to the end of the study treatment follow-up. For this study, the study treatment follow-up is defined as 30 days following the last administration of study treatment.

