### 6.3.2. Treatment group

**Visit 1/ (= Week 0):** Subjects assigned to treatment groups will receive 500 mg IV rituximab (or start azathioprine or mycophenolate mofetil).

The subject will have a physical exam including BVAS and CDA assessments. We will collect information on concomitant medications and AEs. The subject will be asked to complete a quality of life questionnaire. We will collect 24 ml of blood for research purposes when the subject has blood drawn for routine labs. Women of child-bearing potential will undergo a urine pregnancy test as per indicated clinical care. We will enter the results of routine labs as well as results from B cell analysis in our study database.

**Visits 2 to 13** The subject will have a routine clinical evaluation and a BVAS assessment. We will collect information on adverse events, concomitant medications, and medication compliance. Women of child-bearing potential will undergo a urine pregnancy test as per indicated clinical care. We will enter the results of routine labs in our study database.

Subjects in this treatment groups will receive 500 mg IV rituximab at week 22, week 46, week 70 and week 94 with a +/- 1 week window (or continue azathioprine or mycophenolate mofetil). At those visits, prior to infusion, subjects will have 24 ml of blood drawn for research purposes, including analysis of B cell counts.

The visits will be between every 8 weeks to every 12 weeks, based upon the investigator assessment of how closely an individual subject needs to be followed while on maintenance therapy. The means that the subjects could have between 9 visits (if seen every 12 weeks) and 13 visits (if seen every 8 weeks) until the end of the study.

At week 106, all subjects will undergo a CDA assessment by the nephrologist.

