Maintenance therapy with rituximab (Rituxan) is administered at 500 mg IV every 6 months. The visit numbers when the infusion will happen are indicative. Infusion will be scheduled at week 0, week 22, week 46, week 70 and week 94 +/-1 week. Patients who are allergic or intolerant to rituximab or cannot access rituximab will receive maintenance therapy with azathioprine (Imuran) 1.5-2 mg/kg/day or mycophenolate mofetil (CellCept) 1000 mg twice daily. In the maintenance therapy group, B cell subsets will be measured prior to Rituximab infusion until Month 24. For subjects on maintenance therapy with azathioprine or mycophenolate mofetil, B-cell subsets will be measured at week 22, week 46, week 70 and week 94

Xi: Quality of Life questionnaire is administered at infusion visit.

- The last study visit will take place when the 2 years post-randomization timepoint is reached.

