### **General Physical Examination Findings**

At screening, any clinically significant abnormality will be recorded as a preexisting condition. At the end of the study, any new clinically significant findings/abnormalities that meet the definition of an adverse event will also be recorded and documented as an adverse event.

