## **8.2 Recording of Adverse Events**

At each contact with the subject, the investigator will seek information on adverse events by specific questioning and, as appropriate, by examination. Information on all adverse events will be recorded immediately in the source document, and also in the appropriate adverse event module of the case report form (CRF). All clearly related signs, symptoms, and abnormal diagnostic procedure results will be recorded in the source document, though grouped under one diagnosis.

All adverse events occurring during the study period will be recorded. The clinical course of each event will be followed until resolution, stabilization, or until it has been determined that the study treatment or participation is not the cause. Serious adverse events that are still ongoing at the end of the study period will be followed up to determine the final outcome. Any serious adverse event that occurs after the study period and is considered to be possibly related to the study treatment or study participation will be recorded and reported immediately.

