## **8.3 Reporting of Serious Adverse Events and Unanticipated Problems**

All adverse events will be reviewed and recorded in “real time” and reviewed systematically every month by the PI. Adverse events are defined as any untoward or unfavorable medical occurrence in a human subject, including any abnormal sign, symptom, disease, or abnormal laboratory finding temporally associated with the subject’s participation in the research, whether or not considered related to the subject’s participation in the research.

Serious Adverse Events (SAE) will be reported immediately within 1 business days to the UNC IRB, and within 5 business days to the FDA according to the requirements of the IND. Reporting will be done electronically to the UNC IRB (as per current standard operating procedure) and by Fax to both institutions.

For reportable deaths, the initial submission to the UNC IRB may be made by contacting the IRB Director or Associate Director. The AE/Unanticipated Problem Form is required as a follow up to the initial submission.

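### The adverse event period ends 30 days after the last study treatment, which leaves the untreated WATCH arm with no end date and closes early on rituximab, against adverse event collection to 24 months

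*Combined protocol and SAP*

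**What the plan says.** Section 8.1 (Adverse Event Reporting Period) runs AE reporting from the first study procedure to the end of study treatment follow-up, and adds that "the study treatment follow-up is defined as 30 days following the last administration of study treatment". It makes no separate provision for subjects who receive no treatment.

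Section 8.2 uses the same term, study period. All AEs within it are recorded. After it, the section adds only this class: "Any serious adverse event that occurs after the study period and is considered to be possibly related to the study treatment or study participation".

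Other sections point to collection through the end of the study:

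- Section 8.2 also says: "At each contact with the subject, the investigator will seek information on adverse events by specific questioning and, as appropriate, by examination".
- Section 8.1 defines an AE as "any symptom, sign, illness or experience that develops or worsens in severity during the course of the study".
- Section 8.1 (General Physical Examination Findings) says: "At the end of the study, any new clinically significant findings/abnormalities that meet the definition of an adverse event will also be recorded".
- Section 6.3.2, for treatment-group Visits 2 to 13, says: "We will collect information on adverse events, concomitant medications, and medication compliance". Section 6.3.1 has the same instruction for WATCH Visits 2 to 20 and collects AEs at Visit 1. Both schedule tables mark AE collection at every visit from Visit 1.
- Section 8.3 has AEs recorded as they occur and "reviewed systematically every month by the PI", with no end date.
- Sections 4.4.1 and 8.4 keep subjects who relapse or stop therapy in follow-up for 24 months after randomization.

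On the end of follow-up, sections 6.3.1 and 6.3.2 place final assessments at week 106, while the note under the schedule tables says: "The last study visit will take place when the 2 years post-randomization timepoint is reached".

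**The concern.** A reporting period tied to the last dose suits a trial in which every arm is dosed. Here one randomized arm is not. Read literally, section 8.1 has no closing date for WATCH and a closing date before the end of follow-up for rituximab.

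The comparison of harms is the reason for the design: WATCH is meant to spare patients the complications of maintenance immunosuppression. Section 7.2 tabulates AEs by regimen and cohort, and section 8.5.1 asks the DSMB to review AE frequency and severity in one arm against the other. Both need the same observation window in each arm. If WATCH were counted to week 106 and rituximab only to the section 8.1 limit, the shortfall would fall on the maintenance arm and make its toxicity look lower.

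Early stopping adds a further difficulty. Under section 8.4 a Grade 4 infection leads to permanent discontinuation, so in that case the event being studied would itself shorten the period in which later events are recorded.

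**Working it through.** The plan gives no figure of its own on this point. The check is calendar arithmetic.

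**Inputs**

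- Period closes 30 days after the last administration (section 8.1): 30 / 7 = 4.29 weeks.
- Infusions at weeks 0, 22, 46, 70 and 94, each ± 1 week (note under the schedule tables).
- End of follow-up: week 106 (sections 6.3.1 and 6.3.2), or 2 years after randomization (same note), which is 730.5 / 7 = 104.4 weeks if Visit 1 is taken as randomization.

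**Formulas**

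Close = week of last infusion + 4.29. Weeks outside = 106 − close.

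| Last infusion (week) | Period closes (week) | Weeks outside, to week 106 | Share of 106 weeks |
|---|---|---|---|
| 0 | 4.3 | 101.7 | 96% |
| 22 | 26.3 | 79.7 | 75% |
| 46 | 50.3 | 55.7 | 53% |
| 70 | 74.3 | 31.7 | 30% |
| 94 (completer) | 98.3 | 7.7 | 7.3% |

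For a completer infused at week 93, 106 − 97.3 = 8.7 weeks; at week 95, 106 − 99.3 = 6.7 weeks. Measured to 2 years, the completer's gap is 104.4 − 98.3 = 6.1 weeks.

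**Who is affected**

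- *WATCH:* there is no last administration, so the formula has no input and the end is undefined.
- *Rituximab completers:* the last row.
- *Early rituximab stoppers with no replacement drug:* the first four rows. Section 8.4 allows this after a Grade 4 infection or when a subject wishes or needs to stop. A subject with a non-infectious drug reaction is switched to another agent, so these rows need not apply.
- *Azathioprine or mycophenolate taken daily to 24 months:* the 30 days run past the last visit, so nothing is cut off.

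**What falls outside**

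Under section 8.2, events after the close are kept only if they are serious and possibly related. The Post-study Adverse Event paragraph of 8.1 likewise turns on a reasonable relation to the study. On those two texts, new non-serious events and serious events judged unrelated are not kept.

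**Comparison with the schedule**

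WATCH has visits at weeks 100 and 106, both marked for AE collection and both later than week 98.3. The treatment group has AE collection marked at every visit up to the 2-year point. AE collection is not marked at enrollment, at the standard-of-care visits before B cell recovery, or on the phone-call row, so the statement about every visit holds from Visit 1 onward.

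**The case against.** The strongest reply is that one sentence in section 8.1 stands against an otherwise consistent protocol. AEs are collected at every visit from Visit 1, sought at every contact, and followed for 24 months after a subject stops or relapses. A site working from the visit schedule would lose nothing, and WATCH has no early close in any case. That is right about what is likely to be collected. It does not settle the matter: 8.1 is the only explicit definition of the period, 8.2 relies on the same term, and nothing ranks these texts against the schedule. Late events could be collected and still have no clear place in the tables.

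Four stronger readings are tempting, and the documents do not support them.

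- *That the infection outcome will be under-counted.* Infections are a secondary outcome in their own right (section 3.3), and section 7.2 commits to counting all of them without reference to the AE period. The effect on infection counts is uncertain.
- *That the toxicity criterion in section 8.4 is distorted.* It counts serious events. Section 8.3 sends serious events to the IRB within one business day, sets no end date, and defines AEs irrespective of relatedness. The effect is small.
- *That the visit after the last infusion always falls after the period has closed.* With visits 8 to 12 weeks apart, it would come 56 − 30 = 26 to 84 − 30 = 54 days after the close, but only if the week-94 infusion is a numbered visit that restarts the interval. The schedule note calls the infusion visit numbers indicative. The counts in section 6.3.2 (9 visits at 12 weeks, 13 at 8 weeks) put the last numbered visit at 8 × 12 = 12 × 8 = week 96, before the close.
- *That the large gaps are typical.* They apply only to early stoppers without a replacement drug, and the documents give no stopping rates.

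**Conclusion.** The contradiction stands. Section 8.1, with the recording rule in 8.2, gives WATCH no end to its AE period and closes it for rituximab completers about 7.7 weeks (6.7 to 8.7) before week 106. For early stoppers without a replacement drug who remain in follow-up, the gap is 31.7 to 101.7 weeks. This conflicts with the visit schedule, the AE definition, the end-of-study examination rule and the 24-month follow-up.

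The consequence is conditional. If 8.1 is followed, and WATCH is counted to week 106, the AE tables and the DSMB comparison under-count mainly non-serious events on rituximab. In interim DSMB reviews this comes from subjects who have stopped or completed: for a subject still being infused, the last administration has not yet occurred. If the visit schedule governs, no data are lost. Without stopping rates or event rates, the number of events at stake cannot be fixed. The point should be corrected because it leaves the between-arm safety window undefined, but it does not undermine the trial.

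**What to change.** Reconcile the reporting period in 8.1 and the recording rule in 8.2 with section 6.3, the schedule tables, and sections 4.4.1 and 8.4:

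- In 8.1, define one AE period for every subject, from the first study procedure (as now) to the end of the 24-month follow-up, regardless of treatment received or stopped. Name one end point, either week 106 or 2 years after randomization, and use it in both arms.
- In 8.2, make the term study period refer to that definition.
- In 7.2, state that the AE summaries by regimen and cohort, the DSMB comparison in 8.5.1 and the rate in the 8.4 toxicity criterion all use this period in both arms.

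Rates per person-time are optional. They would remove the completers' shortfall if events are evenly spread, but they would not supply the missing end date for WATCH.

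The cost is one sentence in 8.1, a matching word in 8.2 and one sentence in 7.2. No visits or data are added, because the schedule already collects AEs at all 20 WATCH visits and at every treatment-group visit from Visit 1.
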